### 2.3.1 Pharmacokinetic population

The pharmacokinetic population is defined as all randomized participants without deviation that could significantly impact the PK analysis (eg, missing or incorrect IMP injection on PK profile day) and for whom PK data are considered sufficient and interpretable.

All exclusions from the PK population (before and after database lock) will be documented in the CSR together with their reasons.

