- Pharmacokinetic values, antibodies, blood glucose values from samples collected at the sites, as well as HbA1c values are determined in central laboratories blinded to the treatment received.
- Selected AEs (see [Section 10.1.5](#)) will be adjudicated in a blinded fashion.
- The Sponsor study team involved in the data review and analysis will remain blinded to treatment group until database lock:
  - Investigators will be requested not to report unblinded information related to IMP in the electronic case report form (eCRF) and SAE reports,
  - Members of the study team may review compliance with dosing and titration blinded to treatment (monitoring team is not blinded when reviewing),
  - The study team will review data in descriptive statistics without treatment assignment during data review meetings,
  - The unblinded treatment group allocation variable will be included in the clinical study database only at the time of the database lock, to perform the corresponding analyses; summary results by treatment arm will therefore not be available to anyone before database lock.

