### 9.2 SAMPLE SIZE DETERMINATION

Approximately 184 participants will be randomly assigned to either one of the treatment groups, alternating use of SAR341402 and NovoLog or continuous use of NovoLog (in a 1:1 ratio), with a minimum of 146 evaluable participants (73 per treatment group) for the primary PK evaluation expected at the end of the study. If the number of study participants with evaluable PK data is determined to have been reached before all planned 184 participants are randomized, then the study randomization may be stopped sooner.

The sample size calculations are performed based on the expected variability of the primary PK endpoints  $AUC_{last}$ , AUC, and  $C_{max}$  following injection of a predefined, fixed dose of SAR341402 or NovoLog (0.15 U/kg) at Week 16.

A sample size of 146 evaluable participants (73 participants per arm) will ensure that the 90% CI for the estimated treatment ratio is within the acceptance range of [0.8 – 1.25] with at least 90% power; assuming a true ratio between 0.95 and 1.05 (switching arm / non-switching arm) and a total standard deviation on natural log scale of 0.35 or lower.

Sample size calculations were made using SAS® Software Version 9.4.

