### ***Sensitivity analyses***

Exploratory statistical sensitivity analyses may be performed for primary PK parameters. They will be performed in a corresponding manner as the primary analysis, with

- Inclusion of those primary PK parameters affected by major deviations (ie., excluded from primary PK analysis)
- Exclusion of implausible PK parameters and PK parameters suspected to result from apparent but not documented PK irregularities.

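### Discretionary PK-population exclusions may be made after database lock, when treatment arm is known, and the analysis that restores excluded profiles is only optional

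*SAP*

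**What the plan says.** The primary analysis (SAP 2.4.4.1) uses the PK population only. The 90% CIs for the AUClast, AUC and Cmax ratios must all lie within 80-125%.

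SAP 2.3.1 builds that population from randomized participants who meet two conditions. There must be no deviation of potentially significant impact (a missed or wrong injection on the profile day is given as an example), and they must be participants "for whom PK data are considered sufficient and interpretable". It then adds: "All exclusions from the PK population (before and after database lock) will be documented in the CSR together with their reasons".

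Protocol 6.3 sets the limits of blinding: "The Sponsor study team involved in the data review and analysis will remain blinded to treatment group until database lock". It continues: "The unblinded treatment group allocation variable will be included in the clinical study database only at the time of the database lock".

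On sensitivity analyses, SAP 2.4.4.1 says: "Exploratory statistical sensitivity analyses may be performed for primary PK parameters". Two are listed. One is "Inclusion of those primary PK parameters affected by major deviations (ie., excluded from primary PK analysis"; the other is "Exclusion of implausible PK parameters and PK parameters suspected to result from apparent but not documented PK irregularities".

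Some handling is fixed by rule. Early-discontinuation profiles are out of the primary analysis (SAP 2.5.3). AUC values with more than 20% extrapolation are out of all PK statistics (SAP 2.5.7.1). A profile that supports only some parameters keeps those parameters (SAP 2.5.2.1).

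**The concern.** Three features combine. The SAP foresees exclusions after lock. Part of the criterion is judgement, with examples but no closed list and no named decision-maker. From lock onward, the people analysing the data can see both arm and result. Beyond meeting the population definition, the only requirement placed on a post-lock exclusion is that the CSR give the reason. Nothing requires it to be decided blind or confines it to fixed rules.

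The trial is open-label and its main claim rests on three intervals from this one population. An exclusion decided with arm and result in view cannot later be shown to be unrelated to them. A reason in the CSR makes it visible but does not show whether it moved an interval across the boundary. The analysis that would show this need not be run. Its wording also leaves open whether it restores profiles judged uninterpretable or only those with a major deviation.

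**Working it through.** **Which exclusions are exposed**

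| Type of exclusion | Protected by | Exposed? |
|---|---|---|
| Any exclusion by the sponsor team before lock | Team still blinded (Protocol 6.3) | No |
| Early-discontinuation profile | Fixed rule (SAP 2.5.3) | No |
| AUC extrapolated by more than 20% | Fixed rule (SAP 2.5.7.1) | No |
| Partly insufficient profile | Evaluable parameters kept (SAP 2.5.2.1) | No |
| Implausible value, no documented irregularity | Removal listed only as a sensitivity analysis (SAP 2.4.4.1), which implies the value stays in the primary analysis | No |
| Judgement on deviation impact or interpretability, after lock | Reason given in the CSR | Yes |

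**The plan's own figure.** Inputs from Protocol 9.2 and SAP 1.3: 73 per arm, log-SD 0.35, limits 0.80 and 1.25, true ratio 0.95 to 1.05. A parameter passes if d ± t(0.95, df)·s·√(2/73) lies within ln 0.80 to ln 1.25, where d is the difference in log means. Integrating over the distribution of s (df = 143) gives power of 90.3% at a ratio of 0.95, 97.1% at 1.00 and 91.0% at 1.05. With 72 per arm, power at 0.95 is 89.98%. The stated 90% at 73 per arm is reproduced.

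At s = 0.35 the half-width is 0.0959, so an observed ratio must exceed 0.80 × exp(0.0959) = 0.881 to pass.

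**Non-evaluability allowance.** 184 − 146 = 38, or 38/184 = 20.7%; that is 19 per arm, for all reasons together. The documents do not say how many of these would be discretionary or decided after lock.

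**Effect of selective drops.** Simulation with 73 per arm and log-SD 0.35; a pass requires all three parameters to pass. Assumed: AUC/AUClast correlation 0.98, and Cmax correlation with them of 0.5, 0.7 or 0.9. The stratum term is omitted. There were 40,000 to 60,000 trials per cell, with a Monte Carlo standard error of about 0.1 percentage point. A pool is a random set of switching-arm profiles that are open to argument. The lowest in the pool are removed, ranked on the mean of the three logs in (a), on AUC in (b) and on Cmax in (c). Entries are the probability of wrongly passing; ranges cover the three correlations and, in the pool rows, one to three drops.

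| Drops | (a) all three at 0.80 | (b) AUCs only at 0.80 | (c) Cmax only at 0.80 |
|---|---|---|---|
| None | 1.1-2.9% | 3.0-3.7% | 3.5-4.4% |
| Lowest 1-3 of a pool of 5 | 1.4-4.0% | 3.6-5.0% | 4.2-5.8% |
| Lowest 1-3 of a pool of 10 | 1.5-5.2% | 3.9-6.5% | 4.7-7.8% |
| Lowest 3 of all 73 (ceiling) | 3.9-9.0% | 8.7-11.2% | 9.8-12.4% |
| 3 unrelated to the value | 1.1-2.8% | 2.9-3.7% | 3.3-4.5% |

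The largest rises over the matching no-drop cell, in (c) at correlation 0.5, are:

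- pool of 5: 5.8 − 4.4 = 1.4 points;
- pool of 10: 7.8 − 4.4 = 3.4 points;
- ceiling: 12.4 − 4.4 = 8.0 points.

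A separate run of the main cells, with the parameters away from the boundary at a true ratio of 1.00, agreed within simulation error. For three drops from a pool of 10 it gave 2.1-5.2%, 4.9-6.7% and 5.8-7.5%.

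**The case against.** The SAP 2.3.1 sentence is a disclosure rule. It creates no post-lock procedure, and an excluded profile must still fail the population definition, whose examples are factual dosing-day events. That is fair, and it is why the exposure is narrow. The sentence nevertheless foresees post-lock exclusions and adds no safeguard.

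The ceiling row models removing values merely because they are low, which the sensitivity section implies the plan does not do. This stands: that row is a bound, not a scenario. Pools of 5 and 10 have no source in the documents, and ten is 10/19, over half of one arm's whole allowance. With a pool of 5, only case (c) exceeds 5%, by under one point and only at the boundary. This also stands.

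Other safeguards exist. Laboratories are blinded (Protocol 6.3). SAP 2.2 tabulates major deviations by arm and PK-population counts. SAP 2.4.1 requires baseline summaries on the PK population if it falls below 90% of those randomized in either arm. The early-stop option, which applies "If the number of study participants with evaluable PK data is determined to have been reached before all planned 184 participants are randomized", means evaluability must be judged during the trial, so few open decisions may remain at lock. None of these makes a post-lock decision blind or shows its effect on a confidence interval.

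Re-including incorrectly dosed profiles would blur a comparison defined by a fixed dose. This stands in part: a different result would need explanation profile by profile and would not by itself prove bias. It is a diagnostic beside the primary analysis, and the SAP already describes one for major deviations. The scope of that analysis can be read broadly, so the gap there is one of ambiguity.

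**Conclusion.** The concern holds as a minor-to-moderate weakness that is cheap to close. The text permits discretionary exclusions with arm and result known; it does not show that any were intended. Under the assumed pools, the rise in the false-pass probability is at most 1.4 points (pool of 5) or 3.4 points (pool of 10). It matters only when a true ratio sits near the boundary. Exclusions unrelated to the measured value cause no inflation.

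These sizes depend on assumed correlations, pool sizes and drop counts, and on every drop favouring a pass. This is not a demonstrated type 1 error failure. The multiplicity statement in SAP 2.4.4.3 is correct, and the sample size is not in question.

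**What to change.** In SAP 2.3.1, require all discretionary exclusions of participants or parameters to be decided and signed off in a treatment-blinded review before database lock. After lock, allow only:

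- mechanical application of the rules in SAP 2.5.3 and 2.5.7.1; or
- correction of a documented error, with the primary result also shown without that correction.

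If the vendor's PK parameters arrive only after lock, withhold the arm variable from those deciding until they have signed off.

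In SAP 2.4.4.1, make the re-inclusion analysis mandatory and state that it covers every excluded profile with calculable parameters. The 20% extrapolation rule still applies, and early-discontinuation profiles stay in their separate summary (SAP 2.4.4.4). Report exclusions by arm, reason and timing relative to lock.

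The cost is SAP wording, one sign-off and one more model run; blinded data review meetings already exist (Protocol 6.3). There are two drawbacks. The sign-off must fit into the roughly 7 weeks between last patient last visit and lock (SAP 4). A doubtful profile first noticed after lock, with no documented error, stays in the primary analysis.

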### 2.3.2 Safety population

The safety population is defined as all randomized patients who receive at least one dose of IMP, analyzed according to the treatment actually received.

In addition:

- If a patient is dispensed IMP and is lost to follow-up without any documented evidence whether or not the patient took IMP, the patient will be considered exposed and included in the safety population.
- Randomized patients for whom it is unclear whether they took the study medication will be included in the safety population as randomized.
- Non randomized but treated patients will not be part of the safety population, but their safety data will be presented separately.

- Randomized patients having taken at least one kit of SAR341402 will be considered in the switching arm. Patients randomized in the switching arm but having taken only Novolog as treatment will be considered in the non-switching arm.

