Dosing instructions (continued)	
SAR341402 and Novolog will be self-administered by SC injection, in the abdominal wall, buttock, thighs, or upper arms. The area of the injections will be consistent with the habits of the individual participant. Within that area, injection sites will be changed (rotated) at each time. Changes in the area of injection during the study should be avoided as far as possible. It is recommended that, for participants randomized in the IMP switching arm, SAR341402 and Novolog will be injected on different sides (left or right) of the body.
 
The starting dose of NovoLog will be the same (Unit for Unit) as the insulin aspart dose used at the end of the screening or run-in period. If the participant is not on insulin aspart at the end of the screening period, the starting dose will be determined by the Investigator in agreement with the national product label.
 
Changes in the SAR341402 or NovoLog dose will be based on SMPG values and the meal content (when available). It is recommended that doses will be titrated by the participants to achieve a 2-hour PPG of <10 mmol/L (180 mg/dL) while avoiding hypoglycemia, according to the Investigator's instructions. If pre-prandial glucose tests are used, the target range of 4.4 to 7.2 mmol/L (80 to 130 mg/dL) is recommended. For the purpose of this protocol, 2 hours postprandial is defined as 2 hours after the start of the meal.
 
Glycemic targets may be adapted for individual participants, if deemed necessary, eg, due to age, comorbid conditions, and individual considerations. The individual targets will be recorded in source documents.
 
The doses of the meal-time insulin will be reviewed when the basal insulin dose is increased, as they may have to be reduced to avoid daytime hypoglycemia.
 
In the non-switching arm, NovoLog will be administered for 16 weeks.
 
In the switching arm, NovoLog will be administered alternately with SAR341402, starting with NovoLog for 4 weeks, followed by SAR341402 for 4 weeks, then NovoLog for 4 weeks and ending with SAR341402 for the last 4 weeks (ie, a total of 4 x 4-week treatment periods with 3 switches).
 
At the end of Week 16, a 0.15 U/kg of SAR341402 in the switching arm or NovoLog in the non-switching arm will be given in fasting conditions.
 
Mixing of either SAR341402 or NovoLog with other insulin is not allowed nor is dilution.
	
The area for the injection sites for Lantus injection must be different from that of the IMP. The time of injection will be fixed at randomization (Visit 3, Baseline) according to participant and Investigator's preference and maintain (<math>\pm 2</math> hours) throughout the study.
 
The starting dose of Lantus will be the same as the last dose of insulin glargine used at the end of the screening or run-in period. If the participant is not on Lantus at the end of the screening period, the starting dose will be determined by the Investigator in agreement with the national product label.
 
Changes in the Lantus dose are based on fasting/ prebreakfast SMPG values. Lantus doses can be titrated by the participant, according to the Investigator's instructions, to achieve fasting, pre-breakfast SMPG of 4.4 to 7.2 mmol/L (80 to 130 mg/dL), while avoiding hypoglycemia.
 
The increase of the Lantus dose should not exceed 10% of the daily dose of Lantus, unless deemed necessary, according to the clinical judgement of the Investigator.
 
The Investigator may choose to change the rapid-acting insulin doses instead of increasing the basal insulin dose.
 
Whenever the basal insulin dose is changed, the rapid-acting insulin doses need to be reviewed to avoid hypoglycemia.
 
Mixing of Lantus with other insulin is not allowed nor is dilution.
	

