## 1.4 STUDY PLAN

The following figure describes the design of the study:

FPG: fasting plasma glucose; HbA1c: glycated hemoglobin A1c; PK: pharmacokinetics; T1DM: Type 1 diabetes mellitus; \* prior to the screening visit

The study comprises up to 4 periods:

- An up to 14-day screening period
- An up to 12-week run-in period (only for patients not treated with NovoLog and insulin glargine (100 U/mL) for at least 12 weeks before screening)
- A 16-week open-label treatment period:
  - Participants in the non-switching arm will receive NovoLog for 16 weeks,
  - Participants in the switching arm will receive NovoLog for the first 4 weeks, then SAR341402 for 4 weeks, followed by NovoLog for 4 weeks and then SAR341402 for the last 4 weeks.
- A 1-day post-treatment follow-up period.

The study duration per participant will be less than 19 weeks (for participants who do not require the run-in period) and less than 31 weeks (for participants who require the run-in period).

At the end of the 16-week open-label treatment period, patients will have blood sampling, including for PK determination, antibody measurements, HbA1c, and FPG. After blood sampling for the trough PK measurements, patients will receive a single SC injection of 0.15 U/kg SAR341402 (switching arm) or NovoLog (non-switching arm). Subsequently, PK sampling will be conducted for 8 hours according to assessment schedule; see pharmacokinetic flow chart in Section 1.3 of the protocol.

The end of treatment (EOT) is at Visit 7 (Week 16) after randomization. The end of the study (EOS) is a follow-up contact (Visit 8, recorded as Visit 8010 in the clinical database) at the time of Week 16 plus 1 day.

In case of premature permanent investigational medicinal product (IMP) discontinuation, the patients will have a premature treatment discontinuation visit (recorded as Visit 8000 in the clinical database), which will consist of all procedures planned for Visit 7 and is intended to be conducted before the definitive discontinuation of the IMP, or as soon as possible after discontinuation.

Patients who discontinue study intervention should remain in the study, with the remaining visits occurring as scheduled where possible, including the assessments planned in the SoA (see Section 1.3 of the protocol) except serial PK samples that should only be collected at the time of early discontinuation visit and do not need to be repeated at Visit 7 (Week 16).

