### ***Safety observation period***

The observation period for safety data will be divided into 3 main segments:

- The **pre-treatment period** is defined as the time from informed consent up to the time of the first injection of IMP.
- The **on-treatment period** is defined as the time from the first injection of IMP up to the last injection of IMP + 1 day (included).
- The **post-treatment period** is defined as the time from the last injection of IMP + 2 days (included).

Analyses will focus on safety observations during the on-treatment period.

The **on-study observation period** is defined as the time from first injection of IMP until the end of the study (defined as the date of end of participation).

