### **2.3.3 Anti-insulin antibody population**

The AIA population is defined as all patients from the safety population with at least one AIA sample available for analysis (ie, collected during the on-treatment period and at least 8 hours after the last administration of mealtime insulin). Patients will be analyzed according to the treatment actually received.

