### ***Duration of exposure***

The duration of exposure will be the total number of days of administration of the open-label IMP, ignoring temporary drug discontinuation (see [Section 2.5.1](#) for calculation in case of missing or incomplete data).

The duration of exposure to the open-label IMP will be defined in days as:

(Date of the last IMP administration – date of the first IMP administration) + 1

The process described in [Section 2.5.1](#) will be applied to define the date of the last IMP administration. If this date is missing, the IMP exposure duration should be left as missing.

Duration of IMP exposure will be summarized descriptively as a quantitative variable (number, mean, SD, median, minimum, and maximum). The number (n) and proportion (%) of patients exposed to the open-label IMP will be presented by specific time periods for each treatment group in the safety population.

The time periods of interest are grouped as follows:

- Up to 4 weeks,
- >4 to 8 weeks,
- >8 to 12 weeks,
- >12 to 15 weeks,
- >15 to 16 weeks,
- >16 to 24 week,
- >24 weeks.

The cumulative duration of exposure will be described using the following time periods:

- $\geq$  1 day,
- >4 weeks,
- >8 weeks,
- >12 weeks,
- >15 weeks,
- >16 weeks,
- >24 weeks.

Additionally, the cumulative duration of treatment exposure will be provided, defined as the sum of the duration of treatment exposure for all patients, and will be expressed in patient-years.

If the number of patients impacted by COVID-19 is sufficient, the duration of IMP exposure will also be presented by subgroup of COVID-19 impact (Non-impacted, Impacted) (see definition [Section 2.2](#)).

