##### ***Incidence of patients with at least one hypoglycemia***

- Incidence of patients with at least one hypoglycemia will be presented by treatment group for any hypoglycemia and for each hypoglycemia category (as described in [Section 2.1.5.1](#)). Non classified hypoglycemia will be displayed.
- For any hypoglycemia, severe and documented symptomatic hypoglycemia category, incidence of patients with at least one hypoglycemia will be compared for the switching arm versus the non-switching arm using a logistic regression method. The model will include fixed-effect terms for treatment group and the randomization stratum of screening HbA1c (<8%, ≥8). If the logistic model does not converge (e.g., due to sparse data), the randomization stratum may be removed from the model. Odds-ratios and 95% CIs will be displayed using forest plots.
- The number (%) of patients with at least one hypoglycemia leading to permanent IMP discontinuation will be provided by treatment group.
- Incidence of patients with at least one severe hypoglycemia with neuroglycopenic symptoms and/or SMPG <2.8 mmol/L (50 mg/dL) will be summarized.
- If the number of patients impacted by COVID-19 is sufficient, the incidence of patients with at least one hypoglycemia (any, severe, documented symptomatic) will also be

presented by subgroup of COVID-19 impact (Non-impacted, Impacted) (see definition [Section 2.2](#)) and compared between treatment groups using a similar logistic regression model as described above, with added fixed-effect terms for the subgroup and the subgroup-by-treatment interaction. Odds-ratios and 95% CIs will be presented across subgroups using forest plots. The significance level of the subgroup-by-treatment interaction will also be provided for descriptive purpose.

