#### ***2.4.5.2 Analyses of adverse events***

##### ***Generalities***

The primary focus of adverse event reporting will be on treatment-emergent adverse events. Pretreatment and posttreatment adverse events will be described separately.

If an adverse event date/time of onset (occurrence, worsening, or becoming serious) is incomplete, an imputation algorithm will be used to classify the adverse event as pretreatment, treatment-emergent, or posttreatment. The algorithm for imputing date/time of onset will be conservative and will classify an adverse event as treatment emergent unless there is definitive information to determine it is pretreatment or posttreatment. Details on classification of adverse events with missing or partial onset dates are provided in [Section 2.5.1](#).

Adverse event incidence tables will present by SOC and/or PT, the number (n) and percentage (%) of patients experiencing an adverse event. Multiple occurrences of the same event in the same patient will be counted only once in the tables within a treatment phase. The denominator for computation of percentages is the safety population within each treatment group.

Sorting within tables ensures the same presentation for the set of all adverse events within the observation period (pretreatment, treatment-emergent, and posttreatment). For that purpose, the table of all treatment-emergent adverse events presented by SOC and PT sorted by the internationally agreed SOC order and decreasing frequency of PTs within SOCs will define the presentation order for all other tables unless otherwise specified. Sorting will be based on results for the switching arm.

Analyses of all TEAE(s) will be generated for the safety population.

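### SAP 2.3.2 counts switching-arm participants who stop during their assigned first-period NovoLog as non-switching, so arm membership in the safety tables depends on staying on treatment to about Visit 4

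*SAP*

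**What the plan says.** SAP 2.3.2 analyses the safety population by treatment actually received. Its last bullet puts anyone who took at least one SAR341402 kit in the switching arm, and adds: "Patients randomized in the switching arm but having taken only Novolog as treatment will be considered in the non-switching arm". Participants for whom it is unclear whether they took study medication stay as randomised.

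The assigned sequence begins with NovoLog. SAP 1.4: "Participants in the switching arm will receive NovoLog for the first 4 weeks". Protocol 6.1, Table 3: "In the switching arm, NovoLog will be administered alternately with SAR341402, starting with NovoLog for 4 weeks". NovoLog given in the treatment period is investigational product (Protocol 6), so a participant who takes it and stops is in the safety population. SAR341402 first becomes due at Visit 4 (Day 28, window 2 days either way; Protocol 1.3).

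The rule reaches several tables:
- Adverse events (SAP 2.4.5.2): "The denominator for computation of percentages is the safety population within each treatment group".
- Hypoglycemia (SAP 2.4.5.1), including: "The number (%) of patients with at least one hypoglycemia leading to permanent IMP discontinuation will be provided by treatment group".
- Exposure (SAP 2.4.3.1): "patients exposed to the open-label IMP will be presented by specific time periods for each treatment group in the safety population".
- Anti-insulin aspart antibodies (AIA; SAP 2.3.3), a subset of the safety population: "Patients will be analyzed according to the treatment actually received".

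On-treatment time starts at the first injection of either product. The period "is defined as the time from the first injection of IMP up to the last injection of IMP + 1 day (included").

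Protocol 9.3, Table 4 asks for analysis by intervention actually received. It does not say how assigned first-period NovoLog is to be counted.

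**The concern.** The intervention being compared is a sequence, and NovoLog in Weeks 0-4 is correct receipt of it. A switching-arm participant who stops in that period has taken what was assigned and nothing else, yet moves to the comparator. One who continues brings the same NovoLog-only weeks, and any events in them, into the switching arm. What separates the two is a post-randomisation event: staying on treatment long enough to take SAR341402. Nothing comparable happens to a non-switching participant who stops early.

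The safety of switching against not switching is a secondary objective (SAP 1.2.2), and these tables are its main evidence. No as-randomised version of the adverse event, hypoglycemia, exposure or AIA tables is planned. For uncommon outcomes, one or two moved participants can create a visible imbalance between arms that do not differ.

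**Working it through.** The plan gives no figure of its own on this point. The only documented input is 184 randomised 1:1 (Protocol 9.2), that is 184/2 = 92 per arm. All other inputs are assumptions, chosen with the two arms truly identical so that any difference shown comes from the rule.

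**Formula.** Per arm, let n = 92, e = participants who stop before any SAR341402, d = participants with the event, x = those of the d who are early stoppers. The rule moves the e switching-arm early stoppers, so the tables show

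(d − x)/(n − e) for switching against (d + x)/(n + e) for non-switching.

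Switching looks better if and only if (d − x)(n + e) < (d + x)(n − e). Expanding both sides leaves 2de < 2xn, that is **x/e > d/n**: the event must be more frequent in early stoppers than in the arm as a whole.

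**Counts with e = 2** (arms become 90 and 94):

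| Outcome | d | x | True, each arm | Switching | Non-switching | Difference (points) |
|---|---|---|---|---|---|---|
| Stopping before the first switch | 2 | 2 | 2.2% | 0/90 = 0% | 4/94 = 4.3% | −4.3 |
| TEAE leading to discontinuation, one early | 4 | 1 | 4.3% | 3/90 = 3.3% | 5/94 = 5.3% | −2.0 |
| Same, none early | 4 | 0 | 4.3% | 4/90 = 4.4% | 4/94 = 4.3% | +0.2 |
| SAE, one in an early stopper | 3 | 1 | 3.3% | 2/90 = 2.2% | 4/94 = 4.3% | −2.0 |
| SAE, none in an early stopper | 3 | 0 | 3.3% | 3/90 = 3.3% | 3/94 = 3.2% | +0.1 |

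Differences are taken before rounding. For discontinuation outcomes the condition is easily met: with e no larger than 5 and at least one early case, x/e is at least 1/5 = 20%, well above d/n = 4/92 = 4.3%.

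**Any TEAE.** With risk R in continuers and r in early stoppers, switching shows R and non-switching shows [(n − e)R + 2er]/(n + e). With e = 2 and R = 40%:
- r = 10%: (36 + 0.4)/94 = 38.7%, difference +1.3 points.
- r = 40%: difference 0.
- r = 80%: (36 + 3.2)/94 = 41.7%, difference −1.7 points.

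The sign depends on a risk that the documents do not give.

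**AIA incidence.** After baseline, AIA is scheduled at Weeks 8, 12 and 16 (Protocol 1.3). An early stopper therefore counts only if a valid on-treatment sample is taken at discontinuation. Without one the effect is 0. With valid samples, r = 0 and e = 2, R = 20% gives 18/94 = 19.1% (+0.9 points), and R = 30% gives 27/94 = 28.7% (+1.3 points). Both count against switching.

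**Hypoglycemia rate.** Assume continuers contribute 112 days each, and early stoppers 14 days each at twice the rate (continuers' rate = 1).
- Gap between arms after reassignment = 28e/[112(92 − e) + 28e]. For e = 1, 28/10220 = 0.3%; for e = 5, 140/9884 = 1.4%.
- Rise in the non-switching rate itself, which already contains its own e early stoppers. For e = 1, from 10220/10206 to 10248/10220, a rise of 0.14%. For e = 5, from 9884/9814 = 1.0071 to 10024/9884 = 1.0142, a rise of 0.70%.

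**The case against.** The best defence is that someone who never took SAR341402 never switched, that Protocol Table 4 prescribes analysis as treated, and that the SAP states its rule openly and in advance. It stands that the SAP does not contradict the protocol. It does not settle the matter: Table 4 does not require this reassignment, and continuers' NovoLog-only weeks stay in the switching arm, so the rule does not separate exposed from unexposed time either.

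A second objection is that early stopping may be rare. All participants have at least 12 weeks on NovoLog before randomisation (Protocol 4.2), so Weeks 0-4 continue a familiar product in both arms. This stands, and it is why no size can be claimed as expected.

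Third, SAP 2.2 already gives some protection: discontinuation by main reason, including adverse event, on randomised denominators; a listing of participants not treated as randomised; and lists of premature discontinuations with reasons. A reader could probably trace a handful of moved participants. This mitigates but does not correct the adverse event, hypoglycemia or exposure tables. The Kaplan-Meier estimates of discontinuation in the same section do not state which arm assignment they use.

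Fourth, the safety and immunogenicity analyses are descriptive (SAP 2.4.5, 2.4.6.1), and the hypoglycemia odds and rate ratios are exploratory (Protocol 9.4.3, Table 7). This limits the weight of the point.

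A reader might infer that the rule makes switching look safer throughout. The documents do not support that. Early stoppers have less time to accrue events, so unless they stopped because of an event their incidence may be lower, and the rule would then count against switching.

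**Conclusion.** The mechanism is certain from the text: documented early stoppers leave the switching arm although they followed their assigned sequence. The effect tends to favour switching for outcomes tied to discontinuation, once at least one such event falls before SAR341402 is taken. At 2 early stoppers per arm it is about 2 points on TEAEs leading to discontinuation with one early case, and +0.2 points with none. For any TEAE, SAEs and hypoglycemia incidence the direction is unknown. Hypoglycemia rates barely move. AIA incidence is unaffected or would probably move against switching.

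Every size rests on assumed counts, and the effect is nil if no switching-arm participant stops before taking SAR341402. It would also be wrong to infer that the main result is at risk: profiles from premature discontinuation are left out of the primary PK analysis (SAP 2.5.3), and efficacy is analysed as randomised (SAP 2.3.4.1). This is a modest, avoidable artefact in a secondary objective, worth removing because removal costs almost nothing.

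**What to change.** Before database lock, replace the second sentence of the last bullet of SAP 2.3.2 with:

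*Exposed participants randomised to the switching arm who stop IMP before taking any SAR341402, having received only the NovoLog assigned to their first period, remain in the switching arm, including those who stop at or after Visit 4 without taking SAR341402. Reassignment by treatment actually received applies only to participants who received a product outside their assigned sequence.*

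State in 2.3.3 that the AIA population follows the same assignment, and record the change in SAP 1.6. The as-treated principle of Protocol Table 4 stays as it is.

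The cost is one replaced sentence and two short additions, with no new data and no protocol amendment. A separate as-randomised sensitivity table is not needed: after the change, the two assignments would differ only for participants given a product outside their sequence.
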